### 9.2. Adverse Events

All adverse events evaluated will be described. The analysis of AEs will be described the following:

- The number and percentage of patients with at least one adverse event.
- The number and percentage of patients with each adverse event by grades (1-5).

### 9.3. Adverse reactions

All adverse event indicated as related with any study treatment drug in the eCRF adverse event section will be considered. The analysis of toxicities will be provided:

- The number and percentage of patients with at least one toxicity.
- The number and percentage of patients with each toxicity by grade (1-5).

### 9.4. Serious Adverse Events (SAEs)

Serious adverse events listing will be provided the following information:

- Site
- Subject ID
- AE description
- PT Term
- Grade (1-5) NCI CTC AE v5
- Start date
- End date

- AESI (Yes/No)
- Action taken (None / Delay / Dose reduction / Dose interruption / Withdrawn / Not applicable / Unknown / Other)
- Relationship (Palbociclib / Binimetinib / Concomitant medication or procedure / Other / Not related)
- Seriousness criteria (Death / Life-threatening / Hospitalization / Prolonged hospitalization / Persistent or significant disability/incapacity / Congenital anomaly or birth defect / Medically important)
- Outcome (Recovered / Recovered with sequelae / Not recovered/ongoing / Death / unknown)
- DLT (Yes/No)

Serious adverse events analysis includes the following:

- The number and percentage of patients with at least one serious adverse.
- The number and percentage of patients with each serious adverse event by grade (1-5).

## 9.5. Adverse Events of Special Interest (AESI)

Serious adverse events listing will be provided the following information:

- Site
- Subject ID
- AE description
- PT Term
- Grade (1-5) NCI CTC AE v5
- Start date
- End date
- Serious (Yes/No)
- Action taken (None / Delay / Dose reduction / Dose interruption / Withdrawn / Not applicable / Unknown / Other)
- Relationship (Palbociclib / Binimetinib / Concomitant medication or procedure / Other / Not related)
- Seriousness criteria (Death / Life-threatening / Hospitalization / Prolonged hospitalization / Persistent or significant disability/incapacity / Congenital anomaly or birth defect / Medically important)

- Outcome (Recovered / Recovered with sequelae / Not recovered/ongoing / Death / unknown)
- DLT (Yes/No)

Serious adverse events analysis includes the following:

- The number and percentage of patients with at least one serious adverse.
- The number and percentage of patients with each serious adverse event by grade (1-5).

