#### **5.1.3.5.1.6. Clinical Study ARRAY-162-311**

Clinical Study ARRAY-162-311 (MILO study) is an ongoing Phase 3, 2-arm, multinational, randomized, open-label study to evaluate binimetinib (45 mg BID) vs. physician's choice of selected chemotherapies (liposomal doxorubicin, paclitaxel or topotecan) in patients with low-grade serous carcinomas of the ovary, fallopian tube or primary peritoneum who had recurrent or persistent disease after at least 1 prior platinum-based chemotherapy treatment and no more than 3 prior lines of chemotherapy. A total of 360 patients, were to be randomized 2:1 to receive binimetinib or physician's choice chemotherapy. The primary objective was to determine whether treatment with binimetinib prolongs PFS as compared to physician's choice chemotherapy. The study enrollment was discontinued after the planned interim analysis showed that the hazard ratio for PFS crossed the predefined futility boundary.

Enrollment is complete, with a total of 341 patients (228 binimetinib and 113 physician's choice) randomized to treatment and a total of 333 patients (227 patients binimetinib arm and 106 patients physician's choice arm) who received at least 1 dose of binimetinib or physician's choice in the randomized period.

All 227 binimatinib-treated patients (100%) reported at least 1 AE, the most common ( $\geq 30\%$  of patients) of which were diarrhea (71%), nausea (59%), vomiting (56%), blood CK increased (53%), fatigue and edema peripheral (52% each), dermatitis acneiform (49%), abdominal pain (35%) and dry skin (33%). In the crossover period, all 18 binimatinib-treated patients (100%) reported at least 1 AE, and the most frequently reported AEs were similar to those reported in the randomized period.

Two hundred patients (88%) in the binimatinib arm experienced at least 1  $\geq$  Grade 3 AE in the randomized period. Of these AEs  $\geq$  Grade 3, the events reported for  $\geq 10\%$  of patients in the binimatinib arm were blood CK increased (66 patients [29%]), hypertension (27 patients [12%]), vomiting (24 patients [11%]), anemia (23 patients [10%]) and diarrhea (22 patients [10%]). In the crossover period, 14 binimatinib- treated patients (78%) experienced at least 1  $\geq$  Grade 3 AE.

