#### **Ocular AESIs**

Retinopathy excluding RVO events were the most common AESI grouping reported. Retinopathy excluding RVO events reported in  $> 5.0\%$  of patients were vision blurred, retinopathy, subretinal fluid, retinal detachment, visual field defect and macular edema. Events in the RVO grouping were uncommon.

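### SAP 9.5 carries over the serious-event wording of 9.4, so no AESI-specific tabulation is specified and the AESI listing is worded as serious-only

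*SAP*

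**What the plan says.** SAP 9.5 is the only section of the SAP devoted to AESIs, and it has two parts.

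- **Listing.** The lead-in is "Serious adverse events listing will be provided the following information", followed by 13 fields. One of these is a yes/no flag for seriousness.
- **Tabulation.** The lead-in is "Serious adverse events analysis includes the following". The first item is "The number and percentage of patients with at least one serious adverse" (the noun is missing in the SAP itself). The second counts patients with each serious adverse event by grade.

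SAP 9.4, on serious adverse events, has the same two lead-ins and the same two items. Its listing also has 13 fields, one of which is a yes/no AESI flag.

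Elsewhere, SAP 9.2 and 9.3 tabulate all adverse events and all treatment-related events by grade, per patient. SAP 9.1 codes them by system organ class and preferred term. None of these sections separates or groups AESIs. Protocol 12.5.2 plans adverse events by frequency and CTCAE grade and does not mention AESIs. Protocol 11.3.6 describes binimetinib AESIs as groupings of terms. On the eye, for example, it states: "Retinopathy excluding RVO events were the most common AESI grouping reported".

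**The concern.** The SAP's introduction says that it defines the tables, figures and listings to be presented. A programmer who follows 9.5 to the letter would print the serious-event table a second time under an AESI title. The listing under that title would exclude non-serious AESIs. Being of special interest and being serious are different properties: protocol 11.3.6 defines the AESI groupings by type of event, and CK rises and retinal changes are among them.

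At stake is a dedicated view of the toxicities that the protocol itself singles out, in a trial where the safety of the combination is a secondary objective. If the gap is noticed only after lock, the decision on which events count as AESIs would be made with the data in view.

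**Working it through.** The plan states no figure on this point, so the check compares texts. Background figures from the protocol then show how far seriousness can stand in for special interest.

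**1. SAP 9.4 and 9.5 side by side**

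| Element | 9.4 (serious events) | 9.5 (AESI) |
|---|---|---|
| Listing lead-in | names serious events | same sentence |
| Listing fields | 13, including an AESI yes/no flag | 13, with a serious yes/no flag in its place; the other 12 are identical |
| Tabulation lead-in | names serious events | same sentence |
| Item 1 | patients with at least one serious event | same sentence |
| Item 2 | patients with each serious event by grade | same sentence |

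In a serious-only listing, a seriousness flag would read Yes on every line. The swap makes sense only if the 9.5 listing was meant to hold AESIs whether serious or not. The tabulation contains no such clue.

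**2. Any other AESI count in the documents**

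SAP 9.1 to 9.4 and protocol 12.5.2 contain none. The AESI flag appears only in the serious-event listing of 9.4, so as specified it is displayed for serious events only.

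**3. Whether the all-event table can supply the number**

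Not by addition, because one patient can contribute to several terms. The protocol's liver-related AESI grouping contains AST, ALT and GGT increases. In the Japanese phase 1 study (protocol 5.1.3.5.1.2, N = 21):

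- AST: 0.714 × 21 = 15 patients
- ALT: 0.524 × 21 = 11 patients
- GGT: 0.286 × 21 = 6 patients
- Sum of rows: 15 + 11 + 6 = 32, which exceeds the 21 patients treated

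From these rows alone, the number of patients with at least one of the three terms lies anywhere from 15 (the largest row) to 21 (everyone). The same holds for the number with any AESI. In addition, the 9.2 table does not mark which rows are AESIs.

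**4. Whether the serious-event table can stand in**

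These are single-agent binimetinib data from other tumour types, used as illustration only.

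- Study in Chinese patients with NSCLC (protocol 5.1.3.5.1.5, N = 22): CK increase in 0.727 × 22 = 16 patients, serious in 4. A serious-only table shows 4/16 = 25% and leaves out 12.
- Phase 3 study (protocol 5.1.3.5.1.6, N = 227): CK increase in 53%, or 0.53 × 227 ≈ 120 patients, and Grade 3 or higher in 66 (29%). It is absent from the serious events reported in at least 2%. Since 0.02 × 227 = 4.54, it was serious in at most 4 patients, about 4/120 = 3% of those affected.
- Japanese phase 1 study (N = 21): retinal detachment in 0.619 × 21 = 13 patients. Pneumonia was the only serious event in more than one patient, so retinal detachment was serious in at most 1 of the 13.

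**The case against.** The strongest reply is that this is a copying slip with a small consequence. The swapped column reveals the intent of the listing. SAP 9.2 and 9.3 still count every preferred term by grade, serious or not, so CK increase and retinal detachment would be visible. The protocol's safety outcome is the number of patients with each adverse event by CTCAE grade, which 9.2 delivers. The protocol's statistical section asks for no AESI analysis.

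All of that stands, and it rules out some stronger readings that a reader might infer.

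- *AESIs would go unreported, or the safety objective would fail.* The documents do not support this. Only the AESI-specific counts and the non-serious lines of the AESI listing are lost.
- *About 13 of 25 patients (0.53 × 25 = 13.25) would have a CK event against about none in the output.* This rests on the phase 3 study alone. The N = 22 study would give 4/22 × 25 ≈ 4.5 patients with a serious CK event. Patients with a CK event would in any case appear in the 9.2 table. Neither study tested this combination or this disease.
- *The protocol shows that most binimetinib AESIs are non-serious.* Protocol 11.3.6 reports AESIs by frequency and by Grade 3/4, not by seriousness. Step 4 of the working supports the narrower statement for CK increase and retinal detachment in the studies named.

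The reply does not remove the error. The tabulation in 9.5 has no recoverable intent other than its heading, and neither 9.2 nor 9.3 yields the number of patients with an AESI.

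**Conclusion.** The point holds as a specification error of limited reach. As written, the SAP specifies no AESI-specific tabulation. Its AESI listing is worded as serious-only, against the evident intent of its own columns. The missing results are the number of patients with any AESI and with each AESI by grade.

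In the protocol's background examples, a serious-only table would show between about 3% or less (phase 3) and 25% (N = 22 study) of patients with CK increase, and at most 1 of 13 with retinal detachment. These figures assume only that the background data illustrate the gap between serious and special-interest events; they do not forecast rates in this trial. The primary endpoint, the sample size and the protocol-defined safety outcome are not affected. The wording should still be corrected, because the output is wrong as specified and the repair is nearly free.

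**What to change.** In SAP 9.5:

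1. Replace serious adverse event(s) with AESI(s) in both lead-ins and both tabulation items. The items then give the number and percentage of patients with at least one AESI, and with each AESI by grade, and should state that serious and non-serious events are both included.
2. Keep the yes/no seriousness column in the listing.
3. State that AESIs are identified by the AESI yes/no field already named in the 9.4 listing. This presumes that the field is completed for every adverse event and not only for serious ones, which should be confirmed against the eCRF.

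Grouping by the categories in protocol 11.3.6 would make the table easier to read, but it is optional, as is a split by relatedness. The error is corrected without either.

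The cost is a wording change, one corrected table and one corrected listing before database lock. No new data are needed if the flag is collected for all events.
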